PART B STUDY DESCRIPTION

TITLE OF PROTOCOL	EEG changes with meditation: A proposal to analyze EEG changes with a simple, online, guided meditative tool
Principal Investigator	[name] [name]

B1. PURPOSE OF PROTOCOL

The purpose of this study is to assess:

- a) the qualitative EEG measures associated with meditation
- b) the observed difference in EEG changes between novice and experienced meditators
- c) the observed difference in EEG changes between the start and end of 6 weeks of daily meditation

[figure not shown]
B2. SIGNIFICANCE AND BACKGROUND FOR THE STUDY

Meditation refers to a category of self-regulation practices which focus on training attention and awareness in order to bring mental processes under greater voluntary control. Meditation, as therapy, has the potential to improve mental well-being and development in specific capacities such as calmness, clarity, and concentration.¹ Mindfulness is defined in psychological terms as being characterized by paying total attention to the present moment with a nonjudgmental awareness of inner and outer experiences.²

Meditation and current literature:

Studies have shown numerous benefits of meditation techniques. For example, Goyal et al. reported that meditation has a similar effect on anxiety and depression as compared to medication without the side effects.³ Therefore, it is essential to assess the usefulness of incorporating meditation as an adjunctive therapy in perioperative patient care.

In order to study the benefits and efficacy of meditation intervention, it is important to have an objective measure that assesses the quality of meditation. Ahani et al. reported that EEG signals are sensitive to meditation using coherence and synchrony techniques as well as spectral analysis.⁴ The overall effect of meditation is decreased electro-cortical arousal.⁵ Meditators have shown to have higher alpha and theta activities in EEGs than non-meditators.⁶ Focused-attention has shown to produce an increase of gamma activity in the brain.⁷ Studies have also shown that meditation produces different activities at different locations such as increased alpha activity in frontal regions⁸ and posterior regions.⁹

EEG spectral analysis of alpha, beta, and theta waves during meditation. Credits :Ahani et al¹⁰

[figure not shown]
A meta-analysis conducted in 2014 showed the most consistently altered brain regions were the left rostral medial prefrontal cortex, anterior/mid cingulate cortex, anterior insula, primary/secondary somatomotor cortices inferior temporal gyrus, and hippocampus.¹¹ Insula is consistently linked to interoception-awareness of the body's internal and visceral states, including respiration, heart rate, emotional self-awareness, and potentially metacognitive awareness.^{12,13} Somatosensory areas are also altered by meditation.

Neuroimaging studies have shown that there is increased cortical thickening in the left prefrontal lobe cluster as well as increased volume of insula, right temporal, and right angular gyrus.¹⁴ Meditators have also shown to have increased grey matter volume.

Central box represents the value from the lower to upper quartile (25th to 75th percentile). The middle line represents the median. The vertical line extends from the minimum to the maximum value.¹⁴

Experienced and novice meditators:

A recent study has shown that after practicing 5-60 hours of meditation, novice meditators experience structural differences in 7 grey matter and 5 white matter tract regions.¹⁵

Number	Grey Matter areas	White matter areas
1)	Anterior cingulate cortices	Corpus callosum
2)	Posterior cingulate cortices	Superior longitudinal fasciculus
3)	Insular cortex	Sagittal stratum
4)	Temporoparietal junction	Thalamic radiation
5)	Hippocampus	Corona radiata.
6)	Caudate nucleus	
7)	Cerebellum	

A recently published study reports that meditation resulted in effortless awareness in novice and experienced meditators and meditation was associated with lower activity in Posterior Cingulate Cortices (PCC).¹⁵ A recent study has shown that meditation correlates with decreased activity of default mode network¹⁶ as opposed to an increased activity of default mode network associated with mind wandering and self-referential processes.¹⁷

Network integration

A recent study has also assessed the network integration in EEG due to meditation and has found that meditation is associated with increased brain network integration.¹⁵ Such studies demonstrate the possibility of application of real time EEG to associate an objective measure of brain activity with subjective mind states related to meditation. EEG has an excellent temporal resolution and is preferred over fMRI in this study since it is portable and less expensive.

Meditation encompasses a family of complex practices that include yoga meditation, mindfulness meditation, mantra meditation, tai chi, etc. However, the training requirements for these types of meditation are variable including training from a trained teacher. Isha Kriya is a type of meditation that does not involve complicated trainings, rituals or mantras and can be performed anywhere at any time. Isha Kriya is a meditation technique that regulates breathing and produces a positive effect on the mind and body as endorsed by millions of people worldwide.¹⁸ At this time, no studies have been done regarding the EEG changes in the brain during Isha Kriya.

This study will investigate if Isha Kriya produces EEG changes comparable to that of established literature and will look at the differences between the start and the end of a 6 week cycle. This study will also explore the difference in EEG changes between experienced and novice meditators.

B3. DESCRIPTION OF RESEARCH PROTOCOL

A. Study Design – Overview, Methods, Procedures

Study design:

This is a prospective trial enrolling healthy volunteers, including novice meditators and experienced meditators. Subjects will undergo an EEG at baseline and again after 6 weeks. During the 6 weeks, subjects will be asked to meditate twice a day, 12 minutes each time.

Recruitment:

Recruitment will occur via flyers posted at BIDMC and flyers emailed to mediation listservs.

Study procedures:

1) EEG

Subjects will undergo an EEG at baseline and again after 6 weeks (+/- 1 week). During the EEGs, the subjects will be asked to meditate.

The ENOBIO 32 EEG device is an investigational device under US federal law which is a 24-bit EEG data reader at the rate of 500 S/s which comes as a wearable wireless electrophysiology sensor system. It includes spectrogram and 3D visualization in real time of spectral features. It also collects triaxial accelerometer data. These data are stored in microSD offline in Holter mode.¹⁹ This EEG communicates via wireless allowing the subjects to be in a comfortable position and also can reduce the effects of electrical interference. EEG measures brain waves by the following processes:

Pre-processing Signal

Down sampling will be done to eliminate interference from unexpected signals.

After down sampling, Band Pass Filter (BPF) will be used to filter the signals.

Ensemble Average

In this step, signal acquired from every selected channel would be averaged. There are fifteen signals from the instruction that are averaged into one signal representing the instruction.

Short Time Fourier Transform (STFT)

STFT will be used to determine a dominant frequency from the signal of an ensemble average result when the event occurs.

Event Related Desynchronization/Event Related Synchronization

ERD/ERS during event is calculated with the above data.

2) Meditation

Subjects will be introduced to Isha Kriya (IK) meditation. IK is a meditation that can be learned quickly and requires approximately 12 minutes, twice a day of practice. This regimen was chosen because of its simplicity making it an excellent way to introduce meditation to beginners. IK does not incorporate a spiritual or religious focus. [name], the principal investigator of the study, was trained to be an instructor by the Isha Institute of Inner Sciences, a nonprofit foundation located at McMinnville, Tennessee.

At the time of enrollment, [name], or a trained research team member, will provide a brief introduction to IK meditation and review a handout of the meditation instructions. The subjects can utilize the online-guided meditation or follow the instructions on their own.

Preparation: Sit in a cross-legged posture or sit in a chair, spine comfortably erect, hands upon thighs, palms facing up, face slightly upturned, eyes closed, keeping a mild focus between the eyebrows.

Meditation: Slow inhaling and exhaling while mentally focusing on the words "I am not the body" and "I am not even the mind" for 7 minutes; uttering a long "Ahh" sound seven times; sitting for 5 minutes with eyes closed.

Subjects will be asked to practice the meditation twice daily for 12 minutes each session, for approximately 6 weeks. They will be given a meditation diary to complete daily.

	Baseline	After 6 weeks
Group 1 - Novice meditators	Meditation with EEG monitoring	Meditation with EEG monitoring
Group 2 - Experienced meditators	Meditation with EEG monitoring	Meditation with EEG monitoring

Study Monitoring / Adverse Events:

The study interventions are non-invasive and minimal risk. Therefore, we will limit the scope of AE monitoring and reporting to the following:

- All Serious Adverse Events believed to be related to the study procedures
- Unexpected, non-serious Adverse Events believed to be related to the study procedures

B. Statistical Considerations

- Sample Size Justification:** In this pilot study, atleast10 patients who complete both EEGs are required for analysis. In order to achieve this target accrual of 10 patients and also to account for potential dropouts, a total of 15 volunteers will be recruited.
- Data Analysis:** Continuous data will be reported as means \pm standard deviation or median (quartile 1, quartile 3) depending on distribution. Normality will be assessed with the Shapiro-Wilk test. Categorical data will be reported as frequencies and proportions and assessed with a chi-square or Fisher's Exact test as appropriate. SAS 9.4 (SAS Institute Inc., Cary, NC) will be used for all analyses, with two-sided p-values < 0.05 considered statistically significant.

The primary aim of the study is to study the effect of guided meditation on EEG. This will be a descriptive study noting the EEG changes (alpha vs beta), differences in the waveform signals between novices and experienced meditators, and at the beginning and the end of the 6-week period. Secondary analysis is being conducted with collaborators outside of BIDMC. [name], [name] & his subordinate [name] from The University of Houston; will be assisting in the analysis of the EEG data collected. They will be provided with limited de-identified dataset in accordance to the terms of specific Data Use Agreements. No PHI will be shared between the institutions and all data will be completely de-identified before secure transfer to the co-investigators.

Primary endpoint:

- 1) Examine the qualitative EEG measures associated with Isha Kriya meditation
 - Event related potential fields in EEG: amplitude in fT and latency in ms
 - Oscillations: power spectral density and time-frequency oscillations in fT²/Hz

Secondary endpoints:

- 1) Investigate the difference in EEG changes between novice and experienced meditators
- 2) Investigate the difference in EEG changes between the start and end of 6 weeks of daily meditation

C. Subject Selection

This is a descriptive study of healthy volunteers, including novices and expert meditators.

Inclusion criteria:

- 1) 18 years or older
- 2) Novice or expert meditator

Novice meditator: No meditation practice in the previous year and < 20 entire lifetime hours

Expert meditator: Meditation \geq 30 min per day for at least 5 days per week over the past 1 year

Exclusion criteria:

- 1) History of any neurological condition (i.e. Parkinson's disease, Alzheimer's disease, Huntington's disease, brain tumors, brain surgery, or multiple sclerosis)
- 2) History of depression, currently being treated with antidepressants
- 3) History of any psychiatric disorder, within last 5 years (i.e. anxiety, psychosis, posttraumatic stress disorder, attention deficit hyperactive disorder)
- 4) Current use of cognition enhancing medications
- 5) Active history (within the last 5 years) of alcohol or drug abuse (> 10 drinks per week)
- 6) History (within the last 5 years) of stroke/aneurysm
- 7) Recent history (< 3 months) of seizures
- 8) Non-English speaking

Subject Protection

Subjects will not be recruited on the basis of race, ethnicity, or gender. However, it is not clear whether the final study sample will contain a representative spread of the racial and gender makeup. There is no reason to exclude pregnant women from this protocol.

B4. POSSIBLE BENEFITS

We do not anticipate any direct benefit to be gained by the individual subject. Insights gained from this trial may allow us to better understand and interpret results and potentially provide information about the association between meditation and structural and functional brain changes.

B5. POSSIBLE RISKS AND ANALYSIS OF RISK/BENEFIT RATIO

Since this is a feasibility study on healthy individuals, and the intervention is non-invasive EEG, the risks expected to be associated with this study are minimum.

EEG:

Noninvasive EEG monitoring is considered a safe procedure. It has no discomfort and produces no sensation. In addition, there is no risk of electric shock. In rare instances, EEG can precipitate seizures in individuals with a seizure disorder due to flashing of lights or deep breathing.²⁰ EEG will be performed by trained study staff.

Meditation:

The meditation intervention only involves thought and mindful breathing. We do not anticipate any physical risk. The meditation program has not been used in this arena prior to this study. Therefore, there is no published information regarding psychological risk. Additional counseling regarding any psychological or emotional distress stemming from this will be provided by the principal investigator at the request of the subject or family.

Risk of breach of confidentiality: As with any research study, there is a small risk associated with a breach of confidentiality. All research staff for this trial has been extensively trained in how to handle confidential data and how to minimize the possibility of this risk. Data will be completely de-identified and transferred in a secure manner.

Risk/Benefit Ratio: The meditation intervention has no expected risks and the knowledge gained could provide information about the association between meditation and structural and functional brain changes. Research team members will attempt to mitigate any of the possible risks described above.

B6. RECRUITMENT AND CONSENT PROCEDURES

Recruitment

Subjects will be identified by the study team via response to study flyers seeking volunteers. Flyers will be posted throughout the Beth Israel Deaconess Medical Center. Flyers will also be sent to meditation listservs such as Isha.

When interested subjects contact the study team, the study will be discussed and the subject will undergo prescreening for eligibility via phone. If the subject meets eligibility criteria, an appointment for the first EEG will be scheduled.

Consent

When the subject arrives at BIDMC for the first EEG, the study will be discussed and the consent form reviewed with a research team member. The subjects will have the opportunity to ask any and all questions, and are free to decline participation at any time. Written informed consent will be obtained prior to any research procedures. A copy of the signed consent will be provided to the subject and the original will be kept in the research files.

The research team undergoes standardized, rigorous training regarding the informed consent process for research. Within the Center for Anesthesia Research Excellence (CARE) at BIDMC, this training is personally overseen by the Clinical Research Administrator and includes: didactic sessions, mandated attendance at CCI/HSPO seminars related to the informed consent process, shadowing of informed consent in a variety of contexts, trainee-led informed consent conversations with the aid of consenting checklists and accompanied by senior staff member and/or PI, robust feedback sessions, and clear communication when the team member is skilled enough to engage in informed consent discussions without direct supervision. All CARE members, including non-physicians, undergo this training.

Subject Protection

This meditation regimen was chosen because it excels in simplicity and is a great way to introduce meditation to beginners. It does not incorporate a spiritual or religious focus. Subjects who are unable to consent for themselves will be excluded from this study.

B7. STUDY LOCATION

Privacy

Study interactions and procedures will take place in private clinical settings with curtains/doors closed so as to provide privacy and comfort. Every effort will be made to protect the privacy of the participant.

Physical Setting

Subjects will be enrolled at BIDMC. Prescreening will occur via phone. Consent and EEGs will be performed in either the Clinical Research Center (CRC) or Pre-admission Testing (PAT) clinic. Electronic data will be maintained on password-protected computers behind the institutional firewall. Paper records will be maintained in locked file cabinets and secure research offices.

B8. DATA SECURITY

All electronic data will be stored in REDCap and/or on password-protected servers behind the BIDMC firewall. Any data collected on paper will be stored in locked file cabinets or in secure offices. Each subject will be assigned a study-specific ID number. A crosswalk between the participants and their study IDs will be maintained on password-protected computers by members of the research team. Limited information will be retained on patients who are prescreened and do not qualify, or who are approached and declined, for the purposes of generating a CONSORT diagram.

Any transfer of data to outside collaborators will be done by sending Limited Data Sets with date-shifting, using Secure File Transfer. Data will be completely de-identified and transferred in a secure manner. The de-identified data will be loaded in memory drive and/or DVD and send via trackable FedEx or using a Secure File Transfer online. Recipients will work with the data on their secure institutional computers, behind a firewall. All data sharing will be done in accordance to the terms of BIDMC-issued Data Use Agreements.

B9 Multi-Site Studies

N/A – not a multi-site study

Is the BIDMC the coordinating site? Yes No

Is the BIDMC PI the lead investigator of the multi-site study? Yes No

B10 Dissemination of Research Results

Participants will be thanked for their time throughout the study. There is no plan to share the results at the conclusion of this trial.

References:

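### No EEG outside meditation is described, so the primary aim as worded, an effect of meditation on EEG, cannot be estimated at any sample size

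*Combined protocol and SAP*

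**What the plan says.** - **EEG procedure (B3.A, Study procedures, 1) EEG).** There is one EEG at baseline and one at about six weeks. The only instruction on the subject's state is "During the EEGs, the subjects will be asked to meditate".
- **Schedule table (B3.A, 2) Meditation).** Both groups at both times have the same entry, "Meditation with EEG monitoring". Baseline here is a visit, not a resting state. The closing eyes-closed sitting period is a step of Isha Kriya itself.
- **Objective (end of B2).** "This study will investigate if Isha Kriya produces EEG changes comparable to that of established literature".
- **Primary aim (B3.B, Data Analysis).** "The primary aim of the study is to study the effect of guided meditation on EEG". The next sentence calls the study descriptive, and the listed primary endpoint is an examination of EEG measures associated with the practice.
- **First secondary endpoint (B3.B).** "Investigate the difference in EEG changes between novice and experienced meditators". The second is worded in the same way for the start and end of the six weeks.
- **Signal processing (B3.A).** "ERD/ERS during event is calculated with the above data". No event and no reference interval is defined.

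**The concern.** An effect of meditation, or a change that meditation produces, is a difference between two states. The plan records one state. If it is followed exactly, the report can give EEG levels during Isha Kriya but cannot say whether they differ from the same person's EEG when not meditating.

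The two comparisons inherit the problem. A higher expert level during meditation could be a stronger response to meditation or a standing difference. The background in B2 leaves the second open: "Meditators have shown to have higher alpha and theta activities in EEGs than non-meditators". A shift in level from baseline to week 6 cancels stable differences between people, but it cannot show whether resting EEG moved or the response to meditation did.

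The loss is permanent. A novice's untrained resting EEG can be recorded only before the six weeks of practice.

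**Working it through.** **The plan's own figure.** The only sample-size figure is 15 recruited for at least 10 completers. No dropout rate is stated; 15 implies 1 − 10/15 = 33.3%. The point below does not depend on it.

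**Model (an assumption of this review).** For group g and visit v, on the log band-power scale:

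M(g,v) = R(g,v) + S(g,v)

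M is the mean during meditation, R the mean at rest, and S the meditation-minus-rest effect. Two groups and two visits give 4 R's and 4 S's, so 8 parameters.

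**Estimability.** The plan observes only the four M's. For any choice of S, setting R = M − S reproduces the same data, so the data say nothing about S. In matrix terms the design has rank 4 for 8 parameters. Recording rest as well raises the rank to 8. A contrast is estimable if appending it to the design matrix leaves the rank unchanged.

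| Quantity | As planned | With a rest segment |
|---|---|---|
| Meditation minus rest, each group and visit | 0 of 4 | 4 of 4 |
| Group differences (2) and visit differences (2) in that effect | 0 of 4 | 4 of 4 |
| Group and visit differences in level during meditation | 4 of 4 | 4 of 4 |

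The second row is built from the effects in the first, so the first two rows hold four independent quantities, not eight.

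**Illustration (all figures assumed).** Let novices have relative resting alpha 1.00 and a meditation/rest ratio of 1.30, so their level during meditation is 1.30.

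- Experts with 20% higher resting alpha and the same response: 1.20 × 1.30 = 1.56.
- Experts with equal resting alpha and a 20% larger response ratio: 1.00 × (1.30 × 1.20) = 1.56.

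The expert/novice ratio is 1.56/1.30 = 1.20 in both cases. The planned recordings cannot tell them apart.

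**Precision if rest is recorded.** For a paired mean change, the 95% CI half-width is t(0.975, n−1)/√n in SDs of the change. The documents give no SD, so the result stays in SD units.

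- n = 10: 2.262/3.162 = 0.715 SD. The change detectable with 80% power (two-sided 0.05) is about 1.00 SD.
- n = 15: 0.554 SD, with a detectable change of about 0.78 SD.

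**Recording time.** 15 volunteers × 2 visits × 5 minutes = 150 minutes at most.

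**The case against.** The strongest reply is that this is a descriptive pilot whose primary endpoint asks only for the EEG measures associated with Isha Kriya, and the planned recordings deliver that. This stands. The conflict is with the wording of the aim, the B2 objective and the endpoints on changes, all of which promise more than description.

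The secondary endpoints can also be read as week 6 against baseline, and as the group difference in that six-week shift. Both are estimable from meditation levels, and the second cancels stable differences between the groups. That also stands, but neither contrast shows whether resting EEG or the response to meditation moved. Reading the primary aim as the effect of six weeks of practice only turns it into the second secondary endpoint, with no control arm.

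ERD/ERS does need a reference interval, and a pre-event window inside the recording might serve for event-related measures. None is defined, and it would not give meditation against rest.

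Three smaller points are fair. The text is silent on rest rather than excluding it, and a figure after B1 is not shown, so the finding is that none is described. The B2 sentence on alpha and theta does not say that the difference is present at rest; it makes a standing difference plausible, not established. And the rank result follows directly from omitting one state, so its value is in showing exactly which questions are lost.

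**Conclusion.** The concern holds. On the readable text, the primary aim as worded and the question whether Isha Kriya produces EEG changes are not identified: none of the four meditation-minus-rest effects can be estimated, nor any group or visit difference in them. Description of EEG during meditation and comparison of its level remain possible. The conclusion needs no assumed effect size or SD. It rests on taking an effect of meditation to mean a difference from a non-meditating state, and on no such recording being made outside the written plan. It should be settled before the first recording, because the baseline visit cannot be repeated.

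**What to change.** **Preferred.** At both visits, with the cap already on, record about 5 minutes of quiet eyes-closed rest in the same posture before the meditation starts. Make the within-session change in log band power, meditation minus rest, the primary quantity, with its 95% CI. Report it beside the absolute levels in the novice-expert and week-6 comparisons. Define the ERD/ERS event and reference windows.

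**Cost.** At most 150 minutes of recording over the study, with no extra visit, device, staff or subjects.

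**Limits to state in the protocol.** Rest always comes first, so order is not separated from state. Rest controls for closed eyes and posture but not for slow breathing. Experts sitting quietly may drift towards meditation. Change over six weeks still has no control arm.

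**Alternative.** If no rest segment is recorded, reword the primary aim, the B2 objective and the endpoints on EEG changes as description of EEG during Isha Kriya and comparison of its level between groups and visits. This costs only text, but it gives up the question of effect.

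### Does leaving open whether the EEG recordings are guided or self-directed undermine the novice/expert and 6-week comparisons?

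*Combined protocol and SAP*

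**What the plan says.** On the recording itself, section B3.A 1) EEG says "During the EEGs, the subjects will be asked to meditate". The visit table at the end of B3.A 2) gives the same entry, "Meditation with EEG monitoring", for both groups at both visits.

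The only sentence about mode is in B3.A 2) Meditation: "The subjects can utilize the online-guided meditation or follow the instructions on their own". It comes directly after the brief introduction and handout given at enrollment. The description of the technique follows, then the home regimen ("Subjects will be asked to practice the meditation twice daily for 12 minutes each session, for approximately 6 weeks") and the diary ("They will be given a meditation diary to complete daily").

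Two other places bear on mode. The protocol title describes the tool as online and guided. In B3.B, Data Analysis, the primary aim is framed as the effect of guided meditation on the EEG, and the comparisons by experience and over the 6 weeks follow at once. The primary endpoint names Isha Kriya without the word guided.

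**The concern.** The EEG procedure does not name a mode, and another sentence permits two. Read together, they could mean that each subject chooses at each recording. A guide would presumably be heard, since the eyes are closed, and sound may affect an EEG.

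The choice could also follow the lines of the two secondary endpoints. Under B6, consent is taken on arrival for the first EEG, so a novice at baseline may have just met the technique and lean on the guide. By the second EEG the same person has been asked to complete many sessions and may not need it. Experts recruited through meditation listservs may not need it at either visit.

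Mode would then be mixed up with experience or with time. If nobody noted it, the mixing could not be examined afterwards.

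**Working it through.** **What the text supports.** The plan states no figure for guidance, so the first check is a comparison of the places that bear on mode.

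| Place | Bears on | Mode indicated |
|---|---|---|
| Title | whole study | online, guided |
| B3.B, primary aim | EEG comparisons | guided |
| B3.A 1) EEG | recordings | none stated |
| Visit table | recordings | none stated |
| B3.A 2), choice sentence | teaching and practice, by its position | either |
| B3.B, primary endpoint | EEG measures | none stated |

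No line says that mode is free at the recordings. The two lines that tie a mode to the study's EEG purpose both say guided. The choice sentence is not expressly limited to home practice, but it sits outside the EEG procedure and leads into the technique and the daily regimen.

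**What bias would require.** Let g be the effect of guidance on an EEG measure, assumed additive. The documents give no value for g and no share of guided recordings.

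- *Groups compared at one visit:* bias = g × (guided share in novices − guided share in experts). It is 0 if g = 0 or the shares are equal.
- *6-week change, same mode at both visits:* (y2 + g) − (y1 + g) = y2 − y1, so g cancels.
- *6-week change, guided at baseline only:* y2 − (y1 + g) = (y2 − y1) − g. Only subjects who switch contribute.

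**Weight of one switcher.** B3.B plans to recruit 15 and requires at least 10 who complete both EEGs, so there are 10 to 15 completers and 20 to 30 recordings. One switcher moves the pooled mean change by g/15 = 0.067g to g/10 = 0.10g. The same fraction applies to any two-level factor that changes in one subject. The plan's own option of sitting cross-legged or in a chair would give the same number. It measures sample size and says nothing particular about guidance.

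For a single-visit group comparison, one subject's weight is 1/(size of own group). The group split is not given, so no figure follows.

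**Practice between visits.** 2 sessions × 7 days × 6 weeks = 84 sessions. The EEG window of plus or minus 1 week gives 2 × 7 × 5 = 70 to 2 × 7 × 7 = 98. This makes a drift away from the guide conceivable at home. It does not show a change of mode at the recording.

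A false-positive rate could be produced only by assuming g, the guided shares, the group sizes, the within-subject correlation and the test. B3.B names no test for the continuous EEG measures, so such a rate would reflect the assumptions and not the plan.

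**The case for a change.** The strongest case for a change is that a title and an aim state a purpose and are not a recording procedure. The choice sentence is not limited to home practice, and it describes what subjects are told at enrollment, which under B6 falls at the same visit as the first EEG. A descriptive study has particular reason to describe its recording condition, and B3.B still sets a two-sided 0.05 threshold. Outside collaborators working on de-identified data could not report a mode that nobody noted. One sentence and one field per EEG would be cheap, and mode cannot be set after the fact.

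What stands is that the text is silent on mode at the EEG, and writing it down would be tidy. The rest does not carry the point further. Silence in a short protocol does not show that mode goes unrecorded: no EEG session form or case report form is among the documents, and B5 has trained study staff performing the recordings. Nor is fixing one mode clearly better. A guide at every EEG puts sound into all recordings, and subjects who practised alone would be tested at week 6 in a mode they had not practised. Self-directed recordings throughout would sit less well with the stated aim.

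A further argument rests on the ensemble-average step, "There are fifteen signals from the instruction that are averaged into one signal representing the instruction", and on the step "ERD/ERS during event is calculated with the above data". If the instruction were a spoken cue, a self-directed recording might lack it. The text does not say what the instruction or the event is, or that either has to do with the audio guide. That is a separate gap in specification, and it would remain if every recording used the same mode.

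**Conclusion.** No change to the plan follows. This is a missing operational detail, not a wrong rule. The title and primary aim favour guided recordings, the choice sentence reads most naturally as covering home practice, and staff running the sessions can be expected to use one mode.

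Bias in the secondary comparisons needs a real guidance effect, mixed modes at the recordings, and a mix that differs by group or visit. The documents give evidence for none of these. Its size and direction are unknown and it may be zero. A constant additive effect cancels from within-subject change, and the 0.067 to 0.10 weight of a single switcher is a feature of 15 to 10 completers, not of guidance. The study is a pilot described as descriptive, and the comparisons at issue are secondary.

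This conclusion assumes that the choice sentence concerns practice and that the EEG staff do not mix modes systematically by group or visit. If session records showed such a mix, the two secondary comparisons would need to be read with that in mind.
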